10.2	Sample size	47

SUPSI

10.3	Criteria for the statistical use of data in the case of incomplete data sets	47
10.4	Planned analyses	47
10.4.1	Datasets and Data Population	47
10.4.2	Primary Analysis	47
10.4.3	Secondary Analysis	48
10.4.4	Interim analyses	48
10.4.5	Security Analyses	48
10.4.6	Deviations	48
10.5	Drop-outs and missing data	48
11	QUALITY ASSURANCE AND CONTROL	49
11.1	Data Archiving	49
11.1.1	Forms	49
11.1.2	Specification of Forms	49
11.1.3	Archiving the Data	49
11.2	Data Management	49
11.2.1	Data Management System	49
11.2.2	Data Security and Backup	49
11.2.3	Analysis and Archiving	49
11.2.4	Validation of electronic data	50
11.3	Monitoring	50
11.4	Audits and inspections	50
11.5	Confidentiality and data protection	50
11.6	Retention of biological material and health-related data	50
12	PUBLICATION AND DISCLOSURE OF DATA	51
14	FUNDING AND SUPPORT	52
14.1	Financing	52
15	INSURANCE	53
16	REFERENCES	54

SUPSI

Study Synopsis

Sponsor/ Sponsor- Investigator	
Sponsor Thim van der Laan AG [name] [name]
 
Investigator [name], PhD University of Applied Sciences and Arts Southern Switzerland (SUPSI) Department of Business Economics, Health and Social Care Physiotherapy Graubünden [name]

Study Title:	Clinical trial study to investigate the effectiveness of the patello
Short Title / Study ID:	Effectiveness study Patello
Protocol Version and Date:	Version 01 from 05.04.2018
Trial registration:	Cantonal Ethics Committee Zurich
Study category and Rationale	Clinical trial with a medical device of risk category C according to ClinV (Art. 20) The device under investigation, Patello, is an innovative product for passive, continuous mobilization of the patella. It consists of CE certified individual components. As a complete device, the Patello is not yet CE certified.
Clinical Phase:	The Patello device will be tested for its effectiveness in this clinical trial before the clinical phase begins.

SUPSI

Background and Rationale:	Restricted movement of the knee joint hinders the everyday life of the affected person. They can be caused by osteoarthritis or after surgical procedures on the knee joint. The therapy of choice for limited knee mobility is the active and passive mobilization of the knee joint (Art. Genu, Art. Patellofemorale, Art. Tibiofibulare) with involvement of the soft tissue mantle (muscles, connective tissue). Active mobilization is carried out by the patient independently through a specific exercise program. Passive mobilisation is part of physiotherapeutic treatment. The aim of mobilisation is to activate the formation of synovial fluid, to regulate the tone of the muscles and to influence the fibre alignment of the collagen tissue. The Patello device was built to perform passive, continuous mobilization of the patella as part of rehabilitation with limited knee mobility. The area of application and indication is based on the widely used "Kinetec" knee and hip mobilisation splint. What is innovative about the Patello is that only the Art. patellofemoral is mobilized; the patella is moved on its plain bearing in the cranial and caudal directions.
Objective(s):	The aim of this clinical trial is to prove the effectiveness of the patello.
Outcome(s):	Primary outcome: Objectification of the displacement of the patella to cranial and caudal measurement with an imaging ultrasound device (esaote MyLabClassicC, Genoa, Italy, www.esaote.com). Secondary outcome: Subjective well-being of the subject measured by a visual analogue scale (VAS scale 0 - 10). The knee to be tested is determined by lot (randomized) per test person. The outcomes are recorded after 1, after 10, after 20, after 30 and after 50 mobilizations in the caudal deposition position. The entire measurement procedure is carried out 2x in a week per test subject with a 2-day break in between.
Study design:	Clinical effectiveness study

SUPSI

Inclusion/ Exclusion criteria:	
Inclusion Criteria:
 
- Adults aged 18 to 30 years- No surgical interventions and/or current complaints (pain at rest or during exertion) on the musculoskeletal apparatus in the area of the lower extremities- closed, intact skin conditions in the knee and thigh area- Don't be afraid of the intervention 
Exclusion criteria:
 
- Adolescents and adults over 30 years of age- Surgical interventions and/or current complaints (pain at rest or during exertion) on the musculoskeletal apparatus in the area of the lower extremities- No closed, intact skin conditions in the knee and thigh area- Fear of intervention
Preparation	
Subject recruitment
 
The study is being advertised internally at the University of Applied Sciences and Arts Southern Switzerland SUPSI. Interested parties report to the study director in the research laboratory, who gives them the written subject information and the declaration of consent to read at home. The principal investigator verbally explains the objective, procedure and conditions of the study. If the interested party wants to participate in the study, he or she brings the signed declaration of consent to the research manager, who also signs it. If there is any ambiguity on the part of the interested party, questions can be asked at any time. A copy is given to the future test subject. The health questionnaire is then filled out. This clarifies the inclusion and exclusion criteria. If all inclusion criteria are met, the test subject draws a lot to determine the side to be tested. Afterwards, 2 appointments are arranged, which guarantee a 2-day break between the measurements.
 
Subject preparation
 
The test subject wears shorts and is barefoot. He sits down on the treatment table. The backrest is raised so that an upright sitting position can be assumed. The leg to be tested is placed on the patello and fixed according to the product description (Chapter 8). The foot is placed underneath so that the leg can lie relaxed. In a first phase, the contact pressure of the device is calculated based on the well-being of the test subjects. The setting is noted.

SUPSI

	
Measurement procedure
 
This is followed by the 1st measurement (pre-mobilisation). Afterwards, the mobilization pressure is built up individually up to the tolerance limit of the test subject so that a displacement of the patella caudally takes place (2nd measurement). The maximum deflection of the patella to the reference point is determined and the device settings are noted. As described above, further measurements are carried out according to the following scheme: after 10 mobilisations (3rd measurement), after 20 mobilisations (4th measurement), after 30 mobilisations (5th measurement), after 50 mobilisations (6th measurement).
 
The device settings are kept the same for all measurements per subject.

	
Objective Displacement
 
The displacement of the patella due to mobilization is objectified by means of an imaging ultrasound device. In a second step, the distance of the patellar displacement is evaluated using the ultrasound images using special software (OsiriX, www.Osirix-viewer.com).

	
Subjective information on general well-being
 
After each measurement interval, the subjects report their subjective well-being using a visual analogue scale (VAS). The scale is from "0" (maximum well-being) to "10" (maximum discomfort) in cm-steps.

	
Further processing of the data
 
Microsoft Excel from Windows is used for data pooling and the graphical representation of the end data.

Measurements and procedures:	For this study, we use a device (Patello, Srm-Projects GmbH, Chur) that mobilizes the patella by apparatus, passively and continuously.
Control Intervention (if applicable):	There is no control intervention.
Number of Participants with Rationale:	We limit the number of subjects to $n = 30$. According to the g*power calculation, this gives us an effect size of 0.68 with a power of 0.95.
Study Duration:	June 2018 - December 2018
Study Schedule:	June 2018: planned start of measurements December 2018: planned end of measurements

SUPSI

	
Examiner
 
- [name]^{1,2}- [name], Drs.^{1,2}- [name], MSc¹- [name] 
¹ University of Applied Sciences and Arts Southern Switzerland SUPSI, Department of Business Economics, Health and Social Care, Physiotherapy Graubünden, [name]
 
² THIM University of Applied Sciences in Physiotherapy, [name]
 
³ Medical Center Bad Ragaz, [name]

Investigator(s):	
Contact / Director of Studies
 
[name], PhD
 
University of Applied Sciences and Arts Southern Switzerland (SUPSI) Department of Business Economics, Health and Social Care Physiotherapy Graubünden [name] [contact] [contact]

Study Centre(s):	Single Centre Study: Rehabilitation Research Laboratory University of Applied Sciences and Arts Southern Switzerland SUPSI Department of Business Economics, Health and Social Care Physiotherapy Graubünden [name]
Statistical Considerations:	
Patellar displacement during mobilization application by the patello. Repeated measures analysis of variance (MANOVA)
 
A 2-factor analysis is carried out.
 
Factor 1: Intervention Patello
 
Factor 2: Time intervention: Start (pre-intervention, 1st measurement), after a single mobilization (2nd measurement), after 10 (3rd measurement), after 20 (4th measurement), after 30 (5th measurement), after 50 mobilizations (6th measurement).
 
The significance level is set at $P < 0.05$, and distatistical data analysis is carried out using the Statistical Package for Social Sciences (SPSS V. 24) from IBM, New York, USA.

SUPSI

GCP Statement:	This study will be conducted in compliance with the protocol presented here, the current version of the Declaration of Helsinki, the ICH-GCP, ISO EN 14155 (where applicable), and the Swiss Human Research Ordinance HFV.
-----------------------	--

SUPSI

Overview of the study

Knee joint mobility can be limited by arthritic or post-operative functional or structural changes. Reduced knee joint mobility can interfere with the affected person's everyday activities. Active movement of the knee promotes the formation of synovial fluid, which is essential for the supply of cartilage tissue. Passive mobilization techniques as part of a physiotherapeutic treatment release structural blockages and favor the fiber alignment of the collagen tissue.

In order to provide a further passive mobilisation option of the knee joint, specifically Art. Patellofemoral device, independent of therapists, the Patello device was developed. It performs apparatus, passively and continuously mobilization of the patella in the caudal and cranial directions. The movement deflections are determined by the patient independently based on the current tolerability.

Aim of the study

The aim of this study is to determine the effectiveness of the Patello device. We want to prove that the Patello device moves the patella on the patellofemoral bearing.

The primary outcome is the objectification of the displacement of the patella measured with an imaging ultrasound device (esaote MyLabClassicC, Genoa, Italy, www.esaote.com).

As a secondary outcome, the subjective well-being of the subject is recorded, measured using a visual analogue scale (VAS scale 0 - 10).

In order to record a possible positive effect of repetitive mobilization, the measurements are carried out several times: after the positioning of the device (1st measurement, pre-mobilization), after 1 mobilization, after 10 mobilizations, after 20 mobilizations, after 30 mobilizations and after 50 mobilizations (2nd to 6th measurement). The measurements are carried out on 2 days, with a 2-day break in between.

Abbreviations

CEC	Competent Ethics Committee
GCP	Good Clinical Practice
KlinV	Ordinance on Clinical Trials in Human Research Study Schedule

The completion of the measurement series is planned for December 2018, and the completion of the entire project for December 2019.

Table 1: Schedule

June, 2018	July-December, 2018	January-May, 2019	June-December, 2019
Subject Information, Screening, Planning	Data collection and Statistics	Writing the article	Publishing the article

SUPSI

SUPSI

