9.2.3 Sequence of the measurements

After determining the contact pressure, the pre-mobilization measurement is carried out (**1st measurement**). The ultrasound probe is used to visualize a reference point on the patella and at the same time the lateral femoral epicondyle on the thigh and save it as an image. Afterwards, the mobilization pressure is built up individually up to the tolerance limit of the test subject so that a displacement of the patella caudally takes place. The maximum deflection of the patella to the reference point on the thigh is determined, the device settings are noted and transferred to the data sheet (**2nd measurement**).

As described above, further measurements are carried out according to the following scheme: after 10 mobilisations (**3rd measurement**), after 20 mobilisations (**4th measurement**), after 30 mobilisations (**5th measurement**) and after 50 mobilisations (**6th measurement**).

Table 5: Overview of the course of studies

Time	Preparation	Pre	1 Mob.	10 Mob.	20 Mob.	30 Mob.	50 Mob.
Time (min)		5	10	20	30	40	50
Measurement		1.	2.	3.	4.	5.	6.
Subject information	X						
Consent	X						
Demographics	X						
Intervention			X	X	X	X	X
Ultrasound image		X	X	X	X	X	X
Subj. Well-being		X	X	X	X	X	X

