10 STATISTICAL METHODS

10.1 Hypotheses & Factors

Mobilization of the patella in the caudal / cranial direction by the patello – repetitive mobilizations versus one-time mobilization Objective displacement of the patella:

H0 The patella does not shift significantly more during repetitive mobilizations than during a single mobilization by the patello.

H1 The patella shifts significantly more during repetitive mobilizations than during a single mobilization by the patello.

Subjective well-being of the subject:

H0 Subjective well-being does not change significantly more with repetitive mobilizations than with a single mobilization by the patello.

H1 Subjective well-being changes significantly more with repetitive mobilizations than with a single mobilization by the patello.

A 2-factor analysis is carried out.

Factor 1: Intervention

Factor 2: Time intervention: Start (pre-intervention, 1st measurement), after a single mobilization (2nd measurement), after 10 (3rd measurement), after 20 (4th measurement), after 30 (5th measurement), after 50 mobilizations (6th measurement)

Sample size

The planned sample size is $n = 30$ subjects. This size is expedient, time-wise and financially feasible for the study.

10.2 Criteria for the statistical use of data in the case of incomplete data sets

A complete mobilization interval must be completed for the data to be included in the study. If a mobilisation interval (e.g. interval '20 mobilisations', but termination after 15 mobilisations) has to be interrupted, only the previously collected complete mobilisation interval data can be used. This ensures that all data remains homogeneous and comparable. No substitute is sought for the missing mobilization interval data.

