10.3.2 Primary Analysis

The statistical data analysis is carried out by the statistician after completion of the data collection of the entire project.

Repeated measures analysis of variance (MANOVA) A 2-factor analysis is performed.

Factor 1: Intervention

Factor 2: Time intervention: Start (pre-intervention, 1st measurement), after a single mobilization (2nd measurement), after 10 (3rd measurement), after 20 (4th measurement), after 30 (5th measurement), after 50 mobilizations (6th measurement)

The significance level is set at $P < 0.05$, and the statistical data analysis is carried out with SPSS V. 24.

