10.3.3 Secondary Analysis Not

Available.

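### The planned six-level time test does not test the stated hypothesis that repetitive mobilisation shifts the patella more than a single one, and no contrast that would test it is named

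*Combined protocol and SAP*

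**What the plan says.** The hypothesis for the primary outcome in Section 10.1 is "The patella shifts significantly more during repetitive mobilizations than during a single mobilization by the patello". In terms of the schedule, that sets measurements 3 to 6 (after 10, 20, 30 and 50 mobilisations) against measurement 2 (after one).

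The primary analysis, in the synopsis and in Section 10.3.2, is a "Repeated measures analysis of variance (MANOVA") described as two-factor. Factor 1 is the intervention. Factor 2 begins "Factor 2: Time intervention: Start (pre-intervention, 1st measurement), after a single mobilization (2nd measurement") and runs on to 50 mobilisations, six levels in all. There is no control intervention (8.1.2) and no group assignment (7.3), so Factor 1 has one level and only time is left to test. The next entry reads "10.3.3 Secondary Analysis Not", completed on the following line as Available.

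Section 9.2.3 describes the step between measurements 1 and 2: the pressure is built up "up to the tolerance limit of the test subject so that a displacement of the patella caudally takes place".

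The overview gives a different aim: "We want to prove that the Patello device moves the patella on the patellofemoral bearing".

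On sample size, the synopsis says of n = 30: "According to the g*power calculation, this gives us an effect size of 0.68 with a power of 0.95". The sample size text in Section 10 gives no effect size or power and says "This size is expedient, time-wise and financially feasible for the study".

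**The concern.** An overall time test asks whether any of the six means differs from the others. H1 asks something narrower: whether the later measurements exceed measurement 2. Because the six levels include the pre-mobilisation image, and because the procedure is set up to displace the patella by measurement 2, the overall test can be significant through the first mobilisation alone.

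A significant time effect could then be reported as support for H1 when it shows only that the device moves the patella, which is the aim in the overview and not the hypothesis in 10.1. The plan names nothing that would separate the two. The power figure does not settle the matter, because it is given without a test, effect-size index, sidedness or comparison.

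**Working it through.** **1. The plan's own figure.** Inputs: n = 30, effect size 0.68 and power 0.95 (synopsis); alpha 0.05 (10.3.2). Two-sided testing is assumed.

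- Paired t-test, 29 df: noncentrality = 0.68 × √30 = 3.72, critical t = 2.045, power = 0.949. The standardised paired difference (dz) detectable with power 0.95 is 0.681. The figure reproduces.
- A one-sided paired test would give 0.615.
- A two-group F-test with 30 in total also gives 0.949 at f = 0.68, but the trial has no groups.
- The six-level univariate test under sphericity has a detectable f of 0.34 to 0.11 for correlations of 0 to 0.9. The multivariate form has a detectable distance of 0.91. Neither matches 0.68.

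The paired reading is therefore an inference from the arithmetic. The documents do not state it.

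**2. Hypothesis and test side by side.**

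| | Measurements involved |
|---|---|
| H1 (10.1) | 3 to 6 against 2 |
| Aim in the overview | 2 against 1 |
| Primary test (10.3.2) | any difference among 1 to 6 |

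**3. How often the six-level test rejects when H1 is false.** The mean profile is (0, D, D, D, D, D): a shift of D at the first mobilisation and no further gain. D is in SDs of a paired difference. D, the correlations and the equal variances are assumptions; the documents give none of them.

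*Compound symmetry.* An SD of 1 for a paired difference gives an error variance of 0.5. The sum of squared deviations from the mean is 5D²/6, so the noncentrality is 30 × (5D²/6) / 0.5 = 50D². The multivariate test uses F(5, 25), critical value 2.603; the univariate test uses F(5, 145), critical value 2.277.

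*AR(1).* The paired difference between adjacent measurements has SD 1. The noncentrality is 35.0D² at correlation 0.5 and 30.95D² at 0.8.

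| Probability of rejection | D = 0.5 | D = 0.68 | D = 1.0 |
|---|---|---|---|
| Multivariate, compound symmetry | 0.68 | 0.935 | >0.999 |
| Univariate, compound symmetry | 0.77 | 0.97 | >0.999 |
| Multivariate, AR(1) 0.5 | 0.51 | 0.81 | 0.993 |
| Multivariate, AR(1) 0.8 | 0.45 | 0.75 | 0.984 |

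For comparison, the contrast mean(3 to 6) minus 2 rejected in 0.048, 0.051 and 0.050 of 20,000 simulated trials at the three values of D. Measurement 6 minus 2 has a true mean of zero here, so its paired t-test rejects in 5% under normality. About half of those rejections are in the positive direction.

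**4. What a named contrast can detect when H1 is true.** Take a gain of 0.68 over measurement 2 after 50 mobilisations.

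- Measurement 6 minus 2 has power 0.949, whatever happens at measurements 3 to 5.
- Mean(3 to 6) minus 2 has SD √(0.5 × 1.25) = 0.791 under compound symmetry. Its power is 0.995 if the gain is immediate and held, 0.81 if it is graded from 0.17 to 0.68, and 0.21 if it appears only after 50.

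**The case against.** **The power figure is not wrong.** This stands. A reader might infer an arithmetic error or an underpowered trial from the lack of a named test. The documents support neither. The figure reproduces for a paired comparison, which is the natural form of H1, and the feasibility sentence in Section 10 does not contradict it. The power of the six-level test at 0.68 depends on an unstated index, mean profile and correlation. For a graded gain with no first shift, for example, the multivariate test has power 0.935 under compound symmetry, and 0.80 or 0.75 under AR(1) 0.5 or 0.8 with the SD of measurement 6 minus 2 set to 1. The gap is one of reporting.

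**The model could still answer H1.** This also stands. Only the overall test fails to isolate H1; a contrast within the same repeated-measures model would do so. The empty secondary-analysis entry does not forbid one. But 10.1 does not say which of 10, 20, 30 or 50 mobilisations counts, or how the two days combine, so the choice would fall after the data are seen.

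**The rejection rates rest on assumptions.** They do, and they vary: from 0.45 to 0.77 at a shift of 0.5. Section 9.1.2 may also mean that displacement is measured from the pre-mobilisation image, which would make measurement 1 zero by construction. The tabulated rates would then not apply. The argument would survive, because the multivariate test would then ask whether the mean displacements at measurements 2 to 6 are all zero, which is still not H1.

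**Conclusion.** The plan is wrong as written: the primary test in 10.3.2 does not test the hypothesis in 10.1. This follows from the text alone, from the six levels, the pre-mobilisation level among them, the pressure step in 9.2.3 and the absence of any named contrast.

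The size is illustrative. With n = 30, alpha 0.05 and no benefit of repetition, the multivariate test rejects with probability about 0.45 to 0.68 at a first shift of 0.5 SD, 0.75 to 0.935 at 0.68 and 0.98 or more at 1.0, against about 5% for a contrast with measurement 2. This assumes normal errors, equal variances, and compound symmetry or AR(1) correlation of 0.5 to 0.8.

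The data to be collected can answer H1. No shortfall in sample size is shown.

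**What to change.** - **Primary contrast.** In 10.3.2, name one within-subject contrast for displacement that matches H1, tested at two-sided alpha 0.05, with H1 concluded only if the difference is positive. Measurement 6 minus measurement 2 is one example. It keeps power 0.949 at 0.68 for any course in between, but needs the 50-mobilisation interval completed. The mean of measurements 3 to 6 minus measurement 2 is an alternative that does better for an early effect and worse for a late one.
- **Two days.** State how they enter the primary value, for example as the average of the within-day contrasts, and what is done if only one day is complete. Keep any comparison between days, for the lasting or cumulative effects in 4.3 and 9.2.4, as a separate analysis.
- **Six-level analysis.** Keep it as supportive.
- **Power statement.** In the synopsis and Section 10, restate it as follows: 30 evaluable participants give 95% power to detect a mean paired difference of 0.68 SD of the difference for the named contrast, two-sided alpha 0.05.

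Separately, the passages on device settings must be reconciled: the synopsis and 8.3 keep them the same for all measurements per subject, while the aim text in Section 3 and 3.6 redefine them on each measurement day. Contrasts taken within a day can be computed under either reading.

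Cost: n, visits and measurements do not change. The sponsor commits in advance to a shape of effect. Because the primary test changes, the amendment needs review by the ethics committee and Swissmedic (2.10).
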